## **14. Sample size:**

According to the study by Ahmed et al. [7] , the effect size reported for the mean mucositis score was 1.011. We used a power of 80%, alpha of 5% and an allocation ratio of 1:1 to calculate a sample size of 17 subjects per group.

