#### **11. Interventions:**

**Enrolment:** Enrolment is expected to be done within a one-year period. The enrolled patients will be divided randomly into two groups, each consisting of 33 patients.

**Intervention group:** Patients will receive mixture of MEBO three times daily for 14 days

**Control Group:** Patients will receive Benzydamine Hydrochloride spray three times daily for 14 days.

**Follow up:** The patients will be recalled at one week interval for 14 days.

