### 13. Participant timeline

Enrolled patients will be divided randomly into two groups, each consists of 33patients.

**Intervention group:** Patients will receive mixture of Mebo and pumpkin seed oil spray three times daily

**Control Group:** Patients will receive Benzydamine Hydrochloride spray three times daily

**Follow up:** The patients will be recalled at one week interval for 14 days.

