### **III. Ethics and dissemination**

#### **21. Research ethics approval**

After proper study design revision, the study protocol will be presented to the ethical committee for approval.

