#### **22. Protocol amendments**

The protocol will be registered on clinicaltrials.gov in its current form, further amendments will be updated on the system.

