##### **• Research Procedure in brief:**

A random sample of adult patients receiving radiotherapy or chemotherapy and having sign and symptoms of oral mucositis and this. Enrolled patients will be divided randomly into two groups, each consists of 21patients.

**Intervention group:** Patients will receive MEBO three times daily for two week

**Control Group:** Patients will receive ~~Benzydamine~~ Hydrochloride spray three times daily

**Follow up:** The patients will be recalled at one week interval for two week

as there is no treatment of oral mucositis available in Egyptian market

We will offer palliative treatment that will alleviate the pain of oral mucositis

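### Section 14 calculates 17 patients per group, sections 11 and 13 randomise 33, and no stated step leads from one to the other

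*Combined protocol and SAP*

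**What the plan says.** Section 14 (Sample size) rests on one published result: "the effect size reported for the mean mucositis score was 1.011". With 80% power, 5% alpha and 1:1 allocation, these inputs are used "to calculate a sample size of 17 subjects per group". The section does not say whether the test is one- or two-sided, and it mentions no allowance for loss to follow-up.

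Section 11 (Interventions, under enrolment) says: "The enrolled patients will be divided randomly into two groups, each consisting of 33 patients". Section 13 (Participant timeline) repeats the number: "Enrolled patients will be divided randomly into two groups, each consists of 33patients".

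The application form attached to the protocol, in its brief account of the procedure, says: "Enrolled patients will be divided randomly into two groups, each consists of 21patients".

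On ethics review, item 3 of the administrative information dates approval to April 2021. Section 21 on research ethics approval puts the review in the future: "After proper study design revision, the study protocol will be presented to the ethical committee for approval". Section 22 on amendments adds: "The protocol will be registered on clinicaltrials.gov in its current form".

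**The concern.** The number of patients to randomise is a core design figure. It fixes when recruitment is complete, what the ethics committee is asked to accept, and what difference the trial can detect. Here the protocol body randomises 66 patients, its only calculation supports 34, and the attached form says 42.

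Each number has its own consequence. At 17 per group there is no margin for loss. At 33 per group the trial exposes 66 - 34 = 32 more patients than the calculation asks for, with no reason given. Because the trial is open-label (section 17), a target that is not fixed also leaves room to choose when to stop. Registering the protocol as it stands would carry the conflict into the registry.

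**Working it through.** **Inputs.** From section 14: d = 1.011, power 80%, alpha 5%, allocation 1:1. From section 20: t-test or Mann-Whitney test between groups. Numbers per group: 17 (section 14), 33 (sections 11 and 13), 21 (application form).

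**Step 1: reproduce the 17.** The normal approximation gives n = 2(1.960 + 0.842)² / 1.011² = 15.36, so 16 per group. The exact calculation uses the noncentral t distribution with 2n - 2 degrees of freedom and noncentrality d√(n/2). For two-sided 5% it gives n = 16.38, so 17 per group; power is 79.0% at 16 and 81.5% at 17. A one-sided test gives 13. Section 14 is therefore a correct two-sided t-test calculation with no inflation for loss.

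**Step 2: power at each stated number** (two-sided 5% t-test).

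| Per group | Total | Noncentrality at d = 1.011 | Power at d = 1.011 | d detectable with 80% power |
|---|---|---|---|---|
| 17 | 34 | 2.95 | 81.5% | 0.99 |
| 21 | 42 | 3.28 | 89.2% | 0.89 |
| 33 | 66 | 4.11 | 98.1% | 0.70 |

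**Step 3: look for a route from 17 to the other numbers.**

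- Loss allowance alone, 17/(1 - r): 10% gives 19, 20% gives 22, 30% gives 25 and 40% gives 29. If loss were the only link, 33 would imply 1 - 17/33 = 48.5%.
- Power alone: 90% needs 22, 95% needs 27 and 98% needs 33.
- Power and loss together: 27 × 1.2 = 32.4, rounded up to 33.
- A smaller effect: 33 per group gives 80% power at d = 0.70.
- Mann-Whitney planning: dividing 17 by 0.864, the lowest asymptotic efficiency relative to the t-test under a continuous shift, gives 19.7, so 20.
- To reach 21: 17 × 1.2 = 20.4, rounded up to 21. The divisor form at 20% gives 22, and 21 implies 1 - 17/21 = 19.0%.

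So 33 and 21 can each be reached by ordinary planning steps. None of these steps is stated: the available text has no loss rate, no power other than 80%, no effect other than 1.011 and no second calculation.

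**Step 4: which number was approved, and when.** The April 2021 date and the future-tense section 21 disagree about whether review has happened, and neither gives a number of patients. Recruitment starts in January 2022 (section 15) and is expected to take one year (section 11). The submission date is 12/9/2025 (administrative item 2). On these dates, planned recruitment ended before submission.

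**Step 5: the source of 1.011.** Section 14 credits it to reference [7]. Item 7 in the reference list is a best-practice sheet, which the rationale cites for a background statement. None of the 19 listed items has the first author named in section 14.

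**The case against.** The best defence is that nothing has gone wrong statistically. The sections that say how patients are randomised agree on 33, which gives 98.1% power at the assumed effect, and enrolling more than a calculated minimum is not in itself a flaw. This stands, and it limits the consequence. It does not explain why 33 was chosen when the only calculation supports 17.

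The application form is weaker evidence. It is not a protocol section, its title is restricted to radiotherapy-induced mucositis, and it appears to contain struck-through text, so it may be an earlier draft. The statement in administrative item 5 that there is only one version concerns the protocol. The 21 is therefore secondary. The conflict between 17 and 33 lies within the protocol body and does not depend on the form. Some pages were not available for review and could hold a link, though section 14 is where it belongs.

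Three stronger readings are tempting, and the documents do not support them:

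- A reader might infer that the trial is underpowered. At d = 1.011 all three numbers exceed 80% power on the t-test.
- A reader might infer that 33 requires an implausible loss of about 48% over a two-week follow-up (section 11: "The patients will be recalled at one week interval for 14 days") or a 98% power target, and that 21 cannot be derived at all. Step 3 shows other routes to both. The numbers are undocumented, not unreachable.
- A reader might infer from section 21 that ethics review is still pending. The April 2021 date says otherwise. The title in the same administrative block describes a different trial (metformin for oral leukoplakia), so that date, and the submission date beside it, may not belong to this one. The position is unclear rather than settled either way.

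**Conclusion.** The point holds as an internal inconsistency that must be fixed: the protocol randomises 33 per group and justifies 17, with no stated link. It is neither an arithmetic error nor low power. The gap is a total of 66 against 34, with 42 in the attached form. In terms of what the trial is designed to detect with 80% power, it is the difference between 0.99 at 17 per group and 0.70 at 33.

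Confidence is high for 17 against 33 and lower for the weight to place on 21. The power figures assume a two-sided 5% t-test, which section 14 does not state but which is the version that reproduces 17, and they assume that 1.011 is a standardised mean difference. The inference that planned recruitment has ended assumes that the administrative dates belong to this trial.

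**What to change.** State one enrolment target per group: the number the ethics committee approved and, since planned recruitment appears to have ended, also the number actually enrolled. Reconcile sections 11, 13 and 14 and the application form to it, and make clear whether ethics review is complete.

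In section 14, keep the derivation of 17, name it as a two-sided t-test, and add the power at the target:

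- If the target is 33: 98% power for a standardised difference of 1.011, or 80% power for 0.70.
- If the target is 21: 89% power for 1.011, or 80% power for 0.89.

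Give an attrition assumption only if one was actually made at planning; one should not be constructed now to bridge the numbers. Label any figure produced after recruitment as restated afterwards.

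Separately, correct the source of 1.011 in section 14 and the reference list. When doing so, say which scale it refers to, since section 12 names both WHO and OMAS for the first outcome.

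The cost is wording changes and one corrected reference. If the number approved by the ethics committee differs from the target or from the number enrolled, an ethics notification is also needed.

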## **15. Recruitment:**

A random selection of adult patients complaining from signs and symptoms of oral mucositis attending at the clinic of National Cancer Institute will be enrolled by the investigator in the study in a consecutive order starting from January 2022 without any financial incentives.

## **16. Allocation:**

### **16a. Randomization:**

Method of random sequence generation: computerized random number generator

Type of randomization: Simple

Allocation ratio: 1:1.

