#### **10. Eligibility criteria:**

##### **A- Inclusion criteria:**

- 1) Patients having clinical signs of chemotherapy-induced or radiotherapy-induced OM (WHO oral mucositis grading scale: Grade II, III and IV)
- 2) Patients over the age of 18 years
- 3) Patients having no history of allergy, allergic rhinitis and asthma

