### **16c. Implementation:**

[name] will generate the random sequence and perform the allocation concealment while the investigator will enroll and assign participants to interventions.

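### Simple 1:1 randomisation does not guarantee the stated two groups of 33 (an exact split arises in about 10% of trials); the plan should state a total with approximate arms and rule out forcing equality

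*Combined protocol and SAP*

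**What the plan says.** Section 16a gives the allocation method in three lines: "Method of random sequence generation: computerized random number generator", "Type of randomization: Simple" and "Allocation ratio: 1:1". It mentions no blocks, strata or other restriction.

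Section 11 says "The enrolled patients will be divided randomly into two groups, each consisting of 33 patients", and section 13 repeats it: "Enrolled patients will be divided randomly into two groups, each consists of 33patients". Neither calls 33 approximate. Two other sizes appear: the application form has "Enrolled patients will be divided randomly into two groups, each consists of 21patients", and section 14 calculates 17 per group.

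A separate person generates the sequence and conceals it in opaque, numbered envelopes (sections 16b and 16c), but "the investigator will enroll and assign participants to interventions". Section 17 says masking is not possible.

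The inclusion criteria admit "Patients having clinical signs of chemotherapy-induced or radiotherapy-induced OM". Section 20 plans unadjusted t-tests or Mann-Whitney tests between groups.

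**The concern.** Under simple randomisation each patient is allocated independently, so the arm sizes are random. A plan that names this method and also fixes both arms at 33 has not said how the list is made. Either 33 is only a target and the arms will usually differ, or an undocumented step makes them equal.

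In the first case the plan states sizes that will usually be missed, which is a reporting and reproducibility problem. In the second, allocation near the end of recruitment can be worked out by counting. Opaque envelopes do not prevent this when one unmasked person enrols, assigns and knows the target, and selective enrolment would then be possible.

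A related gap is that eligibility identifies the cause of mucositis, but neither the allocation nor the analysis uses it.

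**Working it through.** **Inputs.** Allocation probability 0.5 per patient (section 16a). N = 66 (sections 11 and 13), 42 (application form) or 34 (section 14). Effect size 1.011, power 80%, alpha 5% (section 14); two-sided testing is assumed.

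**1. The plan's own figure.** The normal approximation gives 2 × (1.960 + 0.842)² / 1.011² = 15.4, so 16 per group. The noncentral t gives power 0.790 at 16 and 0.815 at 17. The plan's 17 per group reproduces.

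**2. Chance of an equal split.** P = C(N, N/2) / 2^N.

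| N | Split | P |
|---|---|---|
| 66 | 33/33 | 0.098 |
| 42 | 21/21 | 0.122 |
| 34 | 17/17 | 0.136 |

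At N = 66, a split of 37:29 or worse has probability 38.9%, 38:28 or worse 26.8%, and 41:25 or worse 6.4%. The expected smaller arm is 29.8.

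**3. Cost in power (t-test, effect size 1.011).** At N = 66, power is 98.1% at 33/33, 97.9% at 38:28, 97.5% at 41:25, and 98.0% averaged over simple randomisation. In effective sample size, 38:28 is worth 4 × 38 × 28 / 66 = 64.5 patients, a loss of 2.3%. At N = 34, average power is 80.3% against 81.5% at 17/17.

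**4. If 33/33 were forced.** Let R be the number of final allocations that are fully determined.
- Toss until one arm has 33, then fill the other: P(R = r) = C(65 − r, 32) / 2^(65 − r). The mean is 66 × 0.0978 = 6.5, and R is 5 or more in 61% of trials.
- Shuffle a list of 33 + 33 labels: P(R = r) = 2 × C(65 − r, 32) / C(66, 33). The mean is 66/34 = 1.9, and R is 5 or more in 5% of trials.

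Either way, at least the last allocation is known.

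**5. Predictability of blocks, for comparison.** If a block size 2m became known, 2m/(m + 1) allocations per block would be determined on average. Over 66 patients, blocks of 4 give 16.5 × 4/3 = 22, and blocks of 6 give 11 × 1.5 = 16.5. Varying, undisclosed sizes reduce this but do not remove it.

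**6. Imbalance in cause.** The documents give no share of chemotherapy-induced disease, so it is assumed here. By simulation at N = 66 under simple randomisation, the arms differ in that share by 15 percentage points or more in 27% of trials if exactly 33 of 66 have it. The figure is 24% if 50% is only the expected share, 19% at a 30% share, and about 5% at 10%. Equal arms do not cure this: with exactly 33 of 66 and arms fixed at 33/33, it is 32%.

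**The case against.** The strongest defence is that 33 is a planned target beside a 1:1 ratio, that simple randomisation is legitimate, and that unequal arms cost almost nothing. All of this stands. It reduces the point to an unclear method, but does not remove it, because the text states 33 as a fact and describes nothing that would produce it.

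A reader might infer that late allocations will be predictable and the trial open to selection bias. The documents do not support that. Nothing describes truncating the list, and a separate person prepares the envelopes. The figure of 6.5 belongs to one assumed mechanism; a shuffled list is just as compatible with a computerised generator and gives 1.9.

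A reader might also infer that blocks are plainly better. They are not: untruncated simple randomisation is the least predictable scheme for an unmasked investigator who enrols and assigns, so the choice is a trade-off.

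Nor does chance imbalance in cause confound the comparison. After valid randomisation it is not bias, and the type I error already allows for it. Adjustment remains worthwhile as a matter of precision and interpretation, if cause is prognostic. That is plausible, but the documents do not quantify it. The question disappears if only radiotherapy patients are enrolled, as section 9 and the application form's title and objective suggest.

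**Conclusion.** The inconsistency is real and modest. The stated method does not guarantee the stated arms: an equal split has a 10% chance at 66 patients, and 10 to 14% at any of the three stated group sizes. To say that the method cannot deliver 33/33 would be too strong, since it does so about once in ten. The loss of power is under 1 percentage point at N = 66, even at 41:25, and about 1 point on average at N = 34.

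The predictability risk is conditional on an undocumented step, and its size depends on which step. The imbalance figures for cause rest on assumed shares. The conflict between 33, 21 and 17 does not change the conclusion, but it has to be settled before any total can be written.

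**What to change.** 1. Reconcile the group size across sections 11, 13 and 14 and the application form.
2. Keep simple randomisation, and replace the fixed arms with the total and about half expected per group (for example, 66 in total, about 33 per group). State that the sequence will be neither truncated nor filled to force equality. This costs a sentence and closes the predictable tail.
3. Alternatively, name a restricted method: computer-generated permuted blocks of randomly varying size, withheld from the enrolling investigator. This costs a line of text and a new list, and accepts some added predictability.
4. In either case, reconcile the radiotherapy-only wording (section 9; application form title and objective) with the either-cause wording (inclusion criteria; application form procedure). If both causes are enrolled, add cause as a factor in the between-group analysis in section 20, with levels for chemotherapy, radiotherapy and both, since section 7 allows combined treatment. No new data are needed beyond what eligibility already establishes.
5. Section 15 gives a January 2022 start and section 11 expects a one-year enrolment, while the registry submission is dated 2025. If allocation is already complete, a new list is not possible. The plan should then report the method actually used and whether equality was forced, and still make the analysis change.

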### **16b. Allocation concealment mechanism:**

All randomization numbers will be concealed in separate, sealed, opaque, serially numbered envelopes.

### **16c. Implementation:**

[name] will generate the random sequence and perform the allocation concealment while the investigator will enroll and assign participants to interventions.

## **17. Masking/blinding:**

This will not be possible as treatments are given in different forms

## **C) Data collection, management, and analysis:**

### **18. Data collection methods**

Outcome data will be collected as printed questionnaires, clinical pictures, and written grading. Outcome data will be entered into excel sheets and clinical photos will be downloaded as a soft copy. Data will be backed up with the supervisors.

### **19. Data management:**

Patient data will be stored on safe computers with antivirus software accessed only by the investigators.

## **20. Statistical methods:**

Data will be analyzed using IBM SPSS advanced statistics (Statistical Package for Social Sciences), version 21 (SPSS Inc., Chicago, IL). Descriptive statistics in case of normal distribution will be presented as mean and standard deviation, while if non-normal; median and 25th and 75th percentile will be used. Intergroup comparison will be done using t-test or Mann-Whitney test while Intra-group comparison will be done using student's t- test.

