## **12. Outcomes:**

Outcome measure		Method of measurement	Unit of measurement
1 st Outcome	Clinical improvement	World Health Organization (WHO)scale.(1)  Oral Mucositis Assessment Scale (OMAS).(2)	Numerical rating score
2 nd Outcome	Quality of life	Patient-Reported Oral Mucositis (PROMS questionnaire).(3)	Continuous outcome (Score codes).

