### ***Clinical parameters:***

#### **Clinical improvement of the lesion:**

The clinical data will be scored according to The World Health Organization (WHO)scale(1). It is graded from 0 to 4. If the patient has no signs and symptoms, it is graded as 0. If the patient has painless ulcers, edema, or mild soreness, it is graded as 1. If there is painful erythema, edema, or ulcers but able to eat, it is graded as 2. If there is painful erythema, edema, or ulcers but unable eat, it is graded as 3. If there a requirement for parenteral or enteral support, it is graded as 4

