#### **Quality of life**

The secondary outcomes will be quality of life assessed by PROMS scale.(2)

The PROMS scale consists of 10, 100-mm horizontal visual analogue scales addressing oral functions affected by oral mucositis. Participants will be asked to mark a point on the line that best represents their present intra-oral condition. During the baseline examination and prior to their completion of the actual PROMS scale questionnaire, participants were subjected to a few training test-visual analogue scale questions focused on simple everyday topics to familiarize them with the concept of visual analogue scale assisted measurements(19). The participants will

complete the PROMS questionnaire thrice; baseline, after the first week, and at the end of the study after the second week.

1. Mouth pain (Mouth encompass also lips, cheeks, tongue, gums, palate and throat)	
no pain	worst possible pain
_____	
2. Difficulty speaking because of mouth* sores	
no trouble	impossible to speak
speaking	
_____	
3. Restriction of speech because of mouth* sores	
no restriction	complete restriction of speech
of speech	
_____	
4. Difficulty eating hard foods (hard bread, potato chips etc) because of mouth* sores	
no trouble	impossible to eat hard foods
eating hard foods	
_____	
5. Difficulty eating soft foods (Jello, pudding etc) because of mouth* sores	
no trouble	impossible to eat soft foods
eating soft foods	
_____	
6. Restriction of eating because of mouth* sores	
no restriction	complete restriction of eating
eating	
_____	
7. Difficulty drinking because of mouth* sores	
no trouble	impossible to drink
drinking	
_____	
8. Restriction of drinking because of mouth* sores	
no restriction	complete restriction of drinking
drinking	
_____	
9. Difficulty swallowing because of mouth* sores	
not difficult to	impossible to swallow
swallow	
_____	
10. Change in taste	
no change in	complete change in taste
taste	

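### The PROMS comparison ignores the baseline PROMS score that the trial collects; adjusting for it would probably narrow the confidence interval at little cost

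*Combined protocol and SAP*

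**What the plan says.** Section 20 (Statistical methods) is the only analysis text. Between groups it says "Intergroup comparison will be done using t-test or Mann-Whitney test"; within groups it names Student's t-test. It names no covariate and no visit, and does not say whether follow-up scores or changes from baseline are compared.

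The other relevant statements are:

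- **PROMS.** Under Quality of life, "The PROMS scale consists of 10, 100-mm horizontal visual analogue scales", and participants "complete the PROMS questionnaire thrice; baseline, after the first week, and at the end of the study after the second week". Section 12 labels it a continuous outcome.
- **WHO grade.** Under Clinical improvement of the lesion, "It is graded from 0 to 4". Eligibility (section 10.A) requires "WHO oral mucositis grading scale: Grade II, III and IV", so an entry grade is known for every patient. The PICO table labels the clinical outcome ordinal; section 12 labels it "Numerical rating score".
- **OMAS.** Listed as a clinical measure, with no baseline assessment stated.
- **Randomisation.** Section 16a: "Type of randomization: Simple".
- **Group size.** 17 per group in section 14, 33 in sections 11 and 13, and 21 in the application form.

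**The concern.** Simple randomisation of small groups balances baseline severity only on average. In any one trial the arms can differ by chance, and nothing in the design limits this. If a patient's PROMS score at entry predicts the score two weeks later, an unadjusted test leaves that predictable variation in the error term and the chance imbalance in the estimate. The confidence interval is then wider than the collected data require.

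At stake is the precision of the quality-of-life result and its power for effects smaller than the large one used for planning. The data needed to recover this precision are already in the visit schedule.

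**Working it through.** **Step 1: the plan's own figure.** Section 14 states that "the effect size reported for the mean mucositis score was 1.011", with 80% power, 5% alpha and 1:1 allocation. Taking the test as two-sided (not stated), the exact two-sample t-test has power 0.790 at 16 per group and 0.815 at 17. The stated 17 per group is reproduced, for an unadjusted test.

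**Step 2: inputs for the adjusted analysis.** Group sizes are those in the documents. The baseline-to-follow-up correlation rho is not given, so 0, 0.3, 0.5 and 0.6 are assumed. With N patients in total and one baseline covariate, the variance of the treatment estimate relative to an unadjusted follow-up comparison is

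(1 − rho²) × (N − 3)/(N − 4).

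The second factor is the average price of estimating the slope under chance baseline imbalance. It is 31/30 = 1.033 at 17 per group, 39/38 = 1.026 at 21 and 63/62 = 1.016 at 33.

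**Step 3: precision for PROMS.**

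| rho | Variance ratio, 33 per group | SE change, 33 per group | 33 per group act like | SE change, 17 per group |
|---|---|---|---|---|
| 0 | 1.016 | about +1% | 32.5 | about +2% |
| 0.3 | 0.91 × 1.016 = 0.925 | −4% | 33/0.925 = 36 | −3% |
| 0.5 | 0.75 × 1.016 = 0.762 | −13% | 33/0.762 = 43 | −12% |
| 0.6 | 0.64 × 1.016 = 0.650 | −19% | 33/0.650 = 51 | −19% |

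The SE change is the square root of the variance ratio, minus 1. These ratios do not depend on the treatment effect.

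**Step 4: break-even.** The ratio equals 1 when rho² = 1/(N − 3). This gives rho = 0.18, 0.16 and 0.13 at 17, 21 and 33 per group.

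**Step 5: if changes from baseline were meant.** With equal variances, a change score has variance proportional to 2(1 − rho), against 1 − rho² for analysis of covariance. The ratio is (1 + rho)/2, or 0.65, 0.75 and 0.80 at rho 0.3, 0.5 and 0.6. In large samples the standard error then falls by about 19%, 13% and 11%.

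**Step 6: power, for illustration only.** The documents give no PROMS effect size. At an assumed standardised difference of 0.5 and 33 per group, unadjusted power is about 52%; adjusted power is about 55%, 63% and 70% at rho 0.3, 0.5 and 0.6. To show the cost at rho 0, take 17 per group and 1.011: power is about 80% adjusted against 81.5% unadjusted.

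**Step 7: the WHO grade.** Entry is limited to three grades, which weakens the correlation. As an illustration, assume an underlying correlation of 0.3, 0.5 or 0.7, cut off the lowest 30% of the entry distribution, and use entry mixes of 60/30/10% or 80/15/5% over grades II, III and IV. The observed correlation is then about 0.17–0.19, 0.30–0.33 or 0.46–0.51, and the variance reduction about 3%, 9–11% or 21–26%. In the first case the 3% roughly cancels the 1.6–3.3% cost from step 2, so the net gain is close to nil.

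**The case against.** The strongest objections are these.

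- **The gain rests on an assumed correlation.** True. The documents give none, so a range is shown that includes zero, where adjustment loses a little.
- **Adjustment is not free.** This stands. A reader might infer that the only price is one degree of freedom and that power is untouched at rho 0. Step 2 shows otherwise: the variance rises, and about one power point goes at 17 per group.
- **Power is already ample.** At 33 per group and an effect of 1.011, unadjusted power is about 98%. But section 14 attaches 1.011 to a mean mucositis score, not to PROMS, so it says nothing about power for PROMS. For the same reason, power gains computed at 1.011 should not be presented as PROMS gains. The interval narrows whatever the effect, and the group size is itself unsettled.
- **The sponsor may have meant change scores.** Possible, since the primary outcome is worded as improvement and section 20 is silent. Baseline would then already be used, but less efficiently than in analysis of covariance (step 5).
- **The clear gain is for a secondary outcome.** This stands. A reader might extend the PROMS gain to the WHO grade. The documents do not support that: the grade has five levels, entry is restricted to three of them, and no correlation is given.

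**Conclusion.** The point holds as an avoidable loss of precision for PROMS. A reader might infer that the unadjusted comparison is biased or wrong; it is neither, because it is valid under randomisation.

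For PROMS the standard error would fall by about 4%, 13% or 19% with 33 per group, and by about 3%, 12% or 19% with 17, if rho is 0.3, 0.5 or 0.6. If rho is near zero, variance rises by about 1.5 to 3.5%. These figures assume a linear baseline relation of similar strength in both arms and an unadjusted follow-up comparison as the alternative. The size of the gain cannot be fixed from the documents. Its direction is favourable once rho exceeds about 0.13 to 0.18.

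For the WHO grade, adjustment is optional: the gain may be close to nil and the cost is about one power point. For OMAS there is no stated baseline to adjust for.

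**What to change.** In section 20, for PROMS:

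- Replace the unadjusted between-group test with an analysis of covariance of the week-2 score on treatment and baseline PROMS.
- Report the adjusted difference with a 95% confidence interval.
- Keep the unadjusted test as a sensitivity analysis.
- State how the ten scales form one score. Fixing the model in advance also rules out a later choice between adjusted and unadjusted results, which matters in an unblinded trial.

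Optional and secondary: adjust the week-2 WHO grade for entry grade with one method named in advance, after settling whether the grade is treated as ordinal or numerical. A rank-based method would not give a difference on the grade scale, so the reported estimate must match the method. Leave OMAS unadjusted unless a baseline OMAS is recorded.

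The cost is a few lines of text. The PROMS and WHO changes need no extra patients, visits or measurements. The statistical price is the small loss at low correlation given above.
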